3.2 Exclusion Criteria

Prior and/or concomitant therapies

- ___1. Prior Radium Ra 223 dichloride
- ___2. Prior or concomitant chemotherapy for metastatic or recurrent disease with the following **exceptions**:
- Prior chemotherapy for local primary disease is permitted.

__3. Prior radiation to prior metastatic sites is allowed provided that it is controlled and the total number of metastatic lesions does not exceed 5.

__4. Concomitant radiation treatment to primary prostate site

Patient MRN	Patient Initials (F, M, L):
-------------	-----------------------------

__5. Bilateral orchiectomy. If unilateral orchiectomy, eligible if testosterone >50 ng/ml.

Other illnesses or conditions

__6. Unstable medical comorbidities (i.e. uncontrolled cardiac comorbidities)

__7. Metastases that in the judgment of investigator-radiologist are not amenable to SBRT

__8. History of brain metastases or who currently have treated or untreated brain metastases

__9. Uncontrolled HIV infection

__10. Any other condition that would, in the Investigator's judgment, contraindicate the patient's participation in the clinical study due to safety concerns with clinical study procedures.

Noncompliance

__11. Prospective participants who, in the opinion of the investigator, may not be able to comply with all study procedures (including compliance issues related to feasibility/logistics).

Eligibility Confirmed* by (Choose as applicable):	Print Name	Signature	Date
 Site PI			
 Authorized study MD			
 Study Nurse			
 Study CRA/ CRC			
 Other: _____			

*Eligibility should be confirmed per institutional policies.

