- To assess overall survival, complete response rate, duration of response, and duration of overall complete response and duration of stable disease in patients with oligometastatic castration sensitive prostate cancer who initiated the protocol regimen of ADT with SBRT and radium Ra 223 dichloride.
- To assess long-term toxicities during 5-year follow-up in patients with oligometastatic castration sensitive prostate cancer who initiated the protocol regimen of ADT with SBRT and radium Ra 223 dichloride and received at least one dose of radium Ra 223 dichloride

Exploratory Objective

- To perform exploratory analysis of primary or metastatic tumor mutation patterns in this study population at baseline
- To identify immune system factors in the blood that change during the course of ADT-radiotherapy for metastatic prostate cancer
- To describe the rate of normalization of the total alkaline phosphatase level (defined as a return to a value within the normal range) at the end of protocol therapy in patients oligometastatic castration sensitive prostate cancer with total alkaline phosphatase values above the upper limit of the normal range at baseline
- To analyze the patients who were in consideration for the study and the reason for ineligibility, including radiographic review, PSA value, and treatment window.

Study Design

The SHARP study is a single-center open-label, Phase 2 clinical trial of stereotactic body radiation therapy (SBRT), hormone/androgen deprivation therapy (ADT) and radium Ra 223 dichloride for participants with metastatic castration sensitive prostate cancer.

Participants will initiate ADT (LHRH agonist leuprolide or goserelin, or LHRH antagonist degarelix or relugolix) for 4 weeks and then receive 32 weeks of ADT on protocol for a total of 36 weeks. Concurrent with standard of care ADT on protocol participants will receive 1 cycle of SBRT followed by 6 cycles of radium Ra 223 dichloride. SBRT is limited to ≤ 4 metastatic lesions with at least 1 bone lesion. Treatment cycles will be 28 days. Participants will receive bisphosphonate or RANKL inhibitor bone health agents at the dose and schedule consistent with the treatment of bone metastases or prevention of osteoporosis, starting approximately when the protocol therapy is initiated and ending when the patient reaches testosterone recovery (>50 ng/dL) or at the discretion of the PI.

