- Must have at least 1 bone lesion **AND** each non-visceral lesion should be less than 5 cm
- Visceral lesions will be limited to one lung lesion (< 2cm) or one lymph node; no liver lesions allowed. Lymph nodes allowed provided they are not in a field of prior radiation, and if amenable to SBRT (to be reviewed by PI). (note: locoregional recurrence is not considered a “visceral metastatic lesion”. This is discussed more below)
- Two lesions can be in close proximity (i.e. within 5cm of each other) if they meet radiation SBRT normal tissue toxicity requirements
- *If have untreated primary prostate cancer:* Must undergo debulking prostatectomy at discretion of treating urologist or definitive radiation therapy. Definitive radiation fields to include close proximity lymph nodes at discretion of treating radiation oncologist. Definitive radiation dose at discretion of treating radiation oncologist.
- If had prior treatment to the prostate primary (definitive radiation therapy or prostatectomy, and can include salvage radiation to the prostate bed +/- lymph nodes), no evidence of locally persistent or recurrent prostate cancer on digital rectal exam (DRE) OR imaging studies (CT or MRI).
 - Note: patients with asymptomatic low volume locoregional recurrent disease will be allowed to enroll on this study after discussion with the PI. In the case where the low volume recurrence is amenable to SBRT, it will be included in the SBRT treatment. In the case where the low volume recurrence is not amenable to SBRT based on reirradiation risk, then we will follow these lesions with re-imaging scans and reassess at later time points for further local control. Additionally, if these patients fail only at the untreated site (due to the untreated recurrence not being amenable to SBRT) they will be censored in the primary efficacy analysis at that time.
- Does not have castration resistant disease (i.e. testosterone >50 ng/dl)

- PSA ≥ 0.2 prior to start of androgen deprivation treatment (ADT)
- Patients will be receiving approximately 36 weeks of ADT as part of this trial. The 36 weeks of ADT may start prior to consenting to this study. The patient may join the study at any point of the 36-week period of ADT treatment. .

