- Patients must be willing to receive bisphosphonate or RANKL inhibitor bone health agents at the dose and schedule consistent with the treatment of bone metastases or prevention of osteoporosis, starting approximately from when the patient begins protocol therapy, until the patient's testosterone reaches normal levels or at the discretion of the PI. Patients who are already on a bone health agent separate from the protocol may continue on this treatment regimen and will not be required to start treatment with an additional bone health agent.
- May have received prior hormonal therapy at the discretion of the PI. Patients may have received prior targeted therapy in the context of definitive treatment of a primary tumor.
- Must have refused standard of care treatment for metastatic disease

Main Exclusion Criteria

- Prior Radium Ra 223 dichloride
- Prior or concomitant chemotherapy for metastatic or recurrent disease with the following **exceptions**:
 - Prior chemotherapy for local primary disease is permitted.
- Prior radiation treatment for metastatic disease is allowed provided that it is controlled and the total number of metastatic lesions does not exceed 5.
- Concomitant radiation treatment to primary prostate site
- Bilateral orchiectomy. If unilateral orchiectomy, eligible if testosterone >50 ng/dl.
- Metastases that in the judgment of investigator-radiologist are not amenable to SBRT

Investigational Product Dosage and Administration

Agent/Therapy and Route of Administration	Dose	Timing of administration and planned duration
Stereotactic Body Radiation Therapy (SBRT) via External Beam Radiation via TrueBeam Stx	9Gy x 3 fractions (bone) 5Gy x 5 fractions (lymph node) 10Gyx5 (lung)	Cycle 1 Day 1, then dosing administered minimum every 40 hours over 7 to 21 days during Cycle 1
Radium Ra 223 dichloride via Slow IV over 1 minute	55 kBq/kg	Cycles 2-7 Day 1 of each 28-day cycle
Leuprolide OR goserelin OR degarelix OR relugolix Per package insert/ investigator discretion		For a total of approximately 36 weeks. May start prior to consenting on study.

Clinical Observations and Tests to be Performed

- Medical history and physical exam
- Safety assessments (CBCs and comprehensive chemistry panel)
- PSA, serum alkaline phosphatase, serum testosterone
- CT/ MRI scans
- Correlative tumor tissue and blood

TABLE OF CONTENTS

SECTION	PAGE
Protocol Team	2
Experimental Design Schema	3
Protocol Synopsis	4

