- Note: patients with asymptomatic low volume locoregional recurrent disease will be allowed to enroll on this study after discussion with the PI. In the case where the low volume recurrence is amenable to SBRT, it will be included in the SBRT treatment. In the case where the low volume recurrence is not amenable to SBRT based on reirradiation risk, then we will follow these lesions with re-imaging scans and reassess at later time points for further local control. Additionally, if these patients fail only at the untreated site (due to the untreated recurrence/disease not being amenable to SBRT) they will be censored in the primary efficacy analysis at that time.

__12. Does not have castration resistant disease

- Castration resistance defined as progression of disease despite serum testosterone level of <50 ng/dL

__13. PSA \geq 0.2 prior to start of androgen deprivation treatment

PSA value:

Date:

__14. Patients will be receiving approximately 36 weeks of ADT as part of this trial. The 36 weeks of ADT may start prior to consenting to this study. The patient may join the study at any point of the 36-week period of ADT treatment.

- Only Luteinizing hormone-releasing hormone (LHRH) agonist/antagonist treatment is considered ADT; bicalutamide or other antiandrogens used alone do not count.

Patient MRN	Patient Initials (F, M, L):
-------------	-----------------------------

___15. Patients must be willing to receive bisphosphonate or RANKL inhibitor bone health agents at the dose and schedule consistent with the treatment of bone metastases or prevention of osteoporosis, starting approximately from when the patient begins protocol therapy, until the patient's testosterone reaches normal levels or at the discretion of the PI. Patients who are already on a bone health agent separate from the protocol may continue on this treatment regimen and will not be required to start treatment with an additional bone health agent.

___16. Patients may have received prior hormone therapy at the discretion of the PI. Patients may have received prior targeted therapy in the context of definitive therapy.

___17. Patients may have had one prior systemic non-chemotherapeutic treatment (i.e. immunotherapy, receptor tyrosine kinase inhibitor, antiangiogenic agent, differentiating agent) for recurrent or metastatic disease.

___18. Must have refused standard of care treatment for metastatic disease

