5.0 TREATMENT PROGRAM

5.1 Treatment Program Overview

This is a single-center open-label, Phase 2 clinical trial of radium Ra 223 dichloride in combination with standard of care androgen deprivation therapy (ADT) and stereotactic body radiation therapy (SBRT) for participants with metastatic castration sensitive prostate cancer ([Section 5.3](#)).

Treatment will be administered in an outpatient basis.

SBRT and radium Ra 223 dichloride will be administered in 28 day treatment cycles ([Section 5.2](#)). Up to 7 cycles of protocol therapy is planned in the absence of unacceptable toxicity or disease progression, whichever comes first. If one agent is discontinued due to toxicity, then the participant may continue to receive the other protocol therapy agent(s).

While the participant is on protocol therapy, they will receive bisphosphonate or RANKL inhibitor bone health agents at the dose and schedule consistent with the treatment of bone metastases or prevention of osteoporosis, until their testosterone levels are within the normal range (>50 ng/dL) or at the discretion of the PI.

Participants who end protocol therapy will undergo follow-up ([Section 5.9](#)). Windows for all assessments and treatments are detailed in [Section 11.0](#).

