5.6 Criteria for Removal from Protocol Therapy

Participants will receive protocol therapy until one of the following criteria are met:

- Disease progression despite castration levels of testosterone < 50 ng/dL
- Completion of 7 cycles of protocol therapy
- Participant is deemed intolerant to protocol therapy because of toxicity, despite dose modification/ delay
 - **Note:** Participants may continue to receive ADT as clinically indicated and per investigator discretion if the other study agents are discontinued.
- Withdrawal of consent for future protocol therapy (See [Section 17.5](#))
- General or specific changes in the participant's condition that render the participant unacceptable for further treatment in the opinion of the treating investigator.

Once participants meet criteria for removal from protocol therapy, the participant should then proceed to End of Treatment assessments.

Documentation of the reason for discontinuing protocol therapy and the date effective should be made in the Electronic Health Record (EHR) and appropriate eCRF.

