Thrombocytopenia Grade 3/4 G3: 25,000-<50,000/mm ³ G4: <25,000/mm ³	Radium Ra 223 Dichloride	First occurrence 
 Hold the planned dose Resume when toxicity resolves to ≤ Grade 2 AND 14 days have passed from last platelet transfusion Permanently discontinue study agent if the planned dose is delayed >28 days. Second occurrence 
 Permanently discontinue study agent.
Other Non-hematological toxicities		
≥ Grade 3	Leuprolide Goserelin Degarelix Relugolix	First occurrence 
 Hold next planned dose until toxicity resolves to ≤ Grade 2. Permanently discontinue ADT if the planned dose is delayed > 42 days. 
 Exception: if testosterone level remains in the castrated state (<50 ng/dL), then participant can remain on the study following consultation with the Study PI or designee. Second occurrence 
 Permanently discontinue protocol therapy.
≥ Grade 3	Radium Ra 223 Dichloride	First occurrence 
 Hold next planned dose until toxicity resolves to ≤ Grade 2. Permanently discontinue study agent if the planned dose is delayed > 28 days. Second occurrence 
 Permanently discontinue protocol therapy.
Non-hematological toxicities- UNRELATED		
Any Grade	UNRELATED	
 Maintain treatment with study agent/ regimen. Interruption of protocol therapy is permitted if the investigator consults with the Study PI to determine that this is in the best interest of the participant.

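### Exclusion criterion 5 in Section 3.2 gives the unilateral-orchiectomy testosterone limit in ng/ml, which makes it 100 times the synopsis limit for the same criterion

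*Combined protocol and SAP*

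**What the plan says.** The criterion on orchiectomy appears twice in the current text of the combined protocol and SAP. Both places exclude bilateral orchiectomy and then make an allowance for unilateral orchiectomy:

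- Section 3.2, exclusion criterion 5: "If unilateral orchiectomy, eligible if testosterone >50 ng/ml".
- Protocol Synopsis, Main Exclusion Criteria: "If unilateral orchiectomy, eligible if testosterone >50 ng/dl".

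The other numeric testosterone thresholds are all 50 ng/dL:

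- Synopsis, Study Design: "testosterone recovery (>50 ng/dL").
- Synopsis, Main Inclusion Criteria: "Does not have castration resistant disease (i.e. testosterone >50 ng/dl").
- Section 3.1, inclusion criterion 12: "Castration resistance defined as progression of disease despite serum testosterone level of <50 ng/dL".
- Section 5.1: "until their testosterone levels are within the normal range (>50 ng/dL"). A footnote to the calendar in Section 11.0 uses the same figure and unit.
- Section 5.6: "Disease progression despite castration levels of testosterone < 50 ng/dL".
- Section 6.3, Table 6.3: "if testosterone level remains in the castrated state (<50 ng/dL").

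Section 4.2.3 sets out how Section 3.0 is used. Its completed checklist goes to the data coordinating center, which verifies eligibility from the submitted documents. A participant who does not meet every requirement is not registered.

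**The concern.** Two live statements of one entry rule differ only in the unit, and the difference is a factor of 100. The version that stands alone is the one on the page that staff complete and the coordinating center checks. The synopsis, which agrees with the rest of the protocol, is not the page that Section 4.2.3 asks for.

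The second sentence of criterion 5 is there to admit some patients with a unilateral orchiectomy. With the limit as printed, staff who meet such a patient have two poor choices. They can turn away someone whom the synopsis admits, or register someone who does not meet the written checklist. Under Section 8.1 the second is a deviation unless a single subject exception has been approved beforehand. Reasons for ineligibility are also an exploratory objective (Section 1.3), so an exclusion made on the wrong unit would be carried into that analysis.

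**Working it through.** No design figure in the plan depends on this threshold, so there is nothing to reproduce first. The check is a unit conversion and a comparison of the two rules.

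**Inputs**

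- Checklist limit (Section 3.2, criterion 5): above 50 ng/mL.
- Synopsis limit (Main Exclusion Criteria): above 50 ng/dL.
- Conversion: 1 dL = 100 mL, so a value in ng/mL × 100 is the value in ng/dL.

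**Conversion**

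- Checklist limit in ng/dL: 50 × 100 = 5,000 ng/dL.
- Synopsis limit in ng/mL: 50 / 100 = 0.5 ng/mL.
- Ratio of the two limits: 5,000 / 50 = 100.

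**What each rule does to a patient with a unilateral orchiectomy**

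The documents give no upper bound for testosterone; Section 5.1 describes normal only as above 50 ng/dL. The values from 300 to 2,000 ng/dL below are therefore an assumed range. The other rows show where each rule switches.

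| Testosterone (ng/dL) | In ng/mL | Synopsis rule (>50 ng/dL) | Checklist rule (>50 ng/mL) |
|---|---|---|---|
| 50 | 0.5 | not met | not met |
| 300 | 3 | met | not met |
| 1,000 | 10 | met | not met |
| 1,500 | 15 | met | not met |
| 2,000 | 20 | met | not met |
| 4,999 | 49.99 | met | not met |
| 5,001 | 50.01 | met | met |

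The two rules disagree for every value above 50 and up to 5,000 ng/dL. The whole assumed range lies inside that interval, and the checklist limit is 5,000 / 2,000 = 2.5 times the top of the range.

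**Which statement is the outlier**

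Of the numeric testosterone thresholds listed above, only Section 3.2, criterion 5, is in ng/ml. Section 5.1 already counts a value above 50 ng/dL as within the normal range, which does not fit with an entry limit of 5,000 ng/dL. No other part of the documents corrects or explains the unit.

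**The case against.** The strongest case on the other side is that this is a copy-edit. The synopsis has the matching unit, and so do all the other thresholds, so a reader can recover the intent. Section 4.2.3 has the coordinating center work with the study team during its review, and staff may well apply ng/dL without noticing the slip. All of that bears on how much the point matters, and it stands. It does not remove the contradiction, because the same section bars registration of a patient who fails a written criterion.

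A reader might infer that the documents themselves show every unilateral-orchiectomy patient to be ineligible. They do not. That conclusion needs an upper bound on testosterone, which they do not give, so it holds only under an assumed range. Criterion 5 also says when a unilateral patient is eligible and leaves exclusion below the limit to be implied. That is the natural reading, but it is a reading.

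A reader might also take inclusion criterion 12 in Section 3.1 as a second statement of this rule. It is a different rule, defining castration resistance as progression at a low testosterone level, and it shares only the number and the unit. The true match is the synopsis exclusion criterion.

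Finally, neither version says when testosterone is to be measured. Patients may join at any point of the 36 weeks of ADT, and the Section 11.0 footnotes accept that a pre-ADT value may be missing. A patient already castrate on ADT, with no earlier value, could fail the synopsis limit too. This stands as a limit on what a change of unit achieves.

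**Conclusion.** The point holds as an internal inconsistency of units in an operative eligibility threshold. The factor of 100 is exact and comes from the documents alone, as does the role of the Section 3.0 checklist at registration. The statement that every such patient would meet the synopsis rule and fail the checklist rests on an assumed testosterone range of 300 to 2,000 ng/dL, and on reading criterion 5 as excluding those below its limit.

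Practical impact is low. It is confined to candidates with a unilateral orchiectomy, whose number is not given. Sample size, power, type I error and the endpoint definitions are unaffected. It is worth correcting because the trial needs 25 patients over 66 months (Section 13.3), and an accidental entry barrier brings no benefit.

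**What to change.** Reconcile Section 3.2, exclusion criterion 5, with the synopsis exclusion criterion by changing ng/ml to ng/dl in Section 3.2, and reissue the printed checklist. This restores the unit that the protocol uses everywhere else for testosterone and introduces no new threshold.

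The cost is one unit in one line, which can go into the next amendment. No analysis or sample-size text needs to change.

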4.0 PARTICIPANT ENROLLMENT

4.1 Pre-Enrollment Informed Consent and Screening Procedures

Diagnostic or laboratory studies performed exclusively to determine eligibility for this trial will be done only after obtaining written informed consent. Studies or procedures that were for clinical indications (not exclusively to determine study eligibility) may be used for baseline values and/or to determine pre-eligibility, even if the studies were done before informed consent was obtained. The informed consent process is to be fully documented (see [Section 17.4](#)), and the prospective participant must receive a copy of the signed informed consent document. All screening procedures and their respective windows are detailed in [Section 11.0, Study Activity Calendar](#).

4.2.2 Slot verification and reservation

Designated study staff should call the DCC to verify current dose level (See [Table 5.2](#)), slot availability, and to reserve a slot for a specific prospective subject. Slots can only be held for a limited time.

Eligible subjects must be registered **prior** to start of protocol therapy. Issues that would cause treatment delays should be discussed with the Principal Investigator. If a subject does not receive protocol therapy following registration, the subject's registration on the study may be canceled after discussion with the PI. The Data Coordinating Center should be notified of cancellations as soon as possible.

4.2.3 Registration Process

To register a participant the subsequent procedure is to be followed:

1. The study team should contact the DCC via telephone or email to provide notification regarding the pending registration and communicate desired timeline of the registration, especially if it must be completed promptly to meet the registration window.
2. The protocol nurse or CRC will email a copy of the following documents to the DCC:
 - Completed eligibility checklist (printed from [Section 3.0](#) of the protocol)
 - Signed Informed Consent
 - Signed subject's bill of Rights
 - Signed HIPAA authorization form and
 - Provide copies of source documentation only if not readily available as a finalized record in the COH Electronic Medical Record (EMR).
3. After having received all transferred documentation, the DCC will complete the review the documents to verify eligibility, working with the study team as needed to resolve any missing required source elements. A participant failing to meet all protocol eligibility requirements will not be registered.
4. Once eligibility has been confirmed, DCC staff will register the participant by: assigning a subject accession number, register the subject on study centrally into a COH clinical trials management system (e.g. MIDAS), and enter the subject into the eCRF system, Medidata RAVE.
5. Once registration has been completed, DCC staff will send a Confirmation of Registration Form within 24 hours, including the participant study number and cohort assignment (dose level or expansion cohort) to:
 - The site study team: Principal Investigator, treating physician, protocol statistician, protocol nurse, CRC and COH IDS Pharmacy.
 - the COH sponsor team designees

[figure not shown]
